#### **9.7.2.2 Missing or Incomplete Data and Lost to Follow-up**

There will be no imputation for missing data.

#### **9.7.2.3 Descriptive Analysis**

##### **9.7.2.3.1 Description of Study Enrollment**

Not applicable

##### **9.7.2.3.2 Description of Subject/Patient Characteristics**

*Not applicable*

#### **9.7.2.4 Analysis of the Primary, Secondary, and Exploratory Endpoint(s)**

To reach the primary endpoint ("To assess the impact of the treatment with FOLFOX or FOLFIRI plus anti-EGFR MAbs on patients' health related quality of life"), comparison between the QoL scores (total and partials) at different times will be done and

differences in mean from basal and follow-up times will be tested with T-test (Student T-test) paired data.

EORTC-QLQ C30 score will be calculated in the total population and also in the two subgroups: FOLFOX/FOLFIRI plus panitumumab and FOLFOX/FOLFIRI plus cetuximab.

Differences in mean between the two subpopulation will be tested at different times with T-test.

- To investigate the impact of dermatological adverse events during the treatment with FOLFOX or FOLFIRI plus anti-EGFR MABs on patients' skin satisfaction will be calculated the Dermatology Life Quality Index (DLQI) score.

Differences in mean between the two subpopulation will be tested at different times with T-test.

- To assess the tolerability of administered treatments, Tolerability and compliance to treatments will be described. Their effect on QoL will be evaluated with a multivariate analysis (Anova).
- To describe the adherence to the treatment **with antiEGFR** in terms of dose delays, dose reductions, number of administered cycles, average relative dose intensity of every drug, all these parameters will be described and the single values observed will be compared with the values reported previously, to determine variations .
- Every adverse event occurred will be described with particular attention to dermatologic ones: description, severity and management of the event will be illustrated. Correlation with number of event and treatments (FOLFOX/FOLFIRI plus panitumumab and FOLFOX/FOLFIRI plus cetuximab) will be verify with a multivariate analysis (Anova)
- Will be verified the presence of preemptive treatment of skin toxicities, and events of skin toxicities . The correlation between events of skin toxicities, QoL and presence of preemptive treatment will be tested with a multivariate analysis (Logistic)

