## 9.5 Study Size

Generally the impact of treatments on cancer patients' QoL is explored in clinical studies as a marginal aspect: data are not collected systematically and no longitudinal information are available about this aspect. So, no evidence of outcomes is present in literature.

For the above reasons the study sample size is not based on mathematical or hypothesis evaluations, or power estimation, but on feasibility considerations.

- Expected number of subjects presenting selected diseases and respecting inclusion/exclusion criteria
- Enrolment capacity and management of patients from centers
- Number of patients with the same disease enrolled in other studies, and their mean follow up time observed

A total sample size of 300 patients has been planned for this study: it is estimated that about 50% (150 pts) of them should be able to complete the QoL questionnaires during the whole treatment period. This population is estimated relevant from the scientific board and useful for a first evaluation on variability of QoL during the whole treatment period.

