#### **9.7.2.1 General Considerations**

All recorded parameters will be described: absolute frequency and percentage will be calculated for qualitative variables, while mean, standard deviation, median, first and third quartile will be used to summarize quantitative variables.

The population will be analyzed totally and stratified for treatment (FOLFOX plus panitumumab and FOLFOX plus cetuximab).

The level of significance will be set to  $p < 0.05$ . No interim analyses are planned for this study.

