#### **9.7.2.5 Sensitivity Analysis**

Not applicable

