#### **9.7.2.5.3 Sensitivity Analysis for Residual Confounding and Bias**

Not applicable

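### The primary by-cycle paired t-tests rest on patients who still have a questionnaire, and no planned analysis addresses attrition or gives the End of Study form a role

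*Combined protocol and SAP*

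**What the plan says.** Section 9.7.2.4 gives one method for change from baseline in the QLQ-C30: "differences in mean from basal and follow-up times will be tested with T-test (Student T-test) paired data". On missing data, section 9.7.2.2 says "There will be no imputation for missing data". Section 9.7.2.5 (Sensitivity Analysis) reads "Not applicable", as do 9.7.2.5.3, headed "Sensitivity Analysis for Residual Confounding and Bias", and 9.7.2.5.4.

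Section 9.5 plans 300 patients and adds that "it is estimated that about 50% (150 pts) of them should be able to complete the QoL questionnaires during the whole treatment period". It gives no effect size or SD; the "study sample size is not based on mathematical or hypothesis evaluations, or power estimation, but on feasibility considerations".

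Sections 9.1 and 9.3 and Table 1 schedule the QLQ-C30 at Day 1 of Cycle 1, repeatedly during treatment, and once at an End of Study Visit within 28 days of stopping the anti-EGFR or withdrawing. Section 9.3 lists the reasons for leaving: anti-EGFR skin toxicity, progression, patient decision, investigator decision and death. It also ends observation at cycle 56. Section 9.9.1, on limitations, discusses only sequential recruitment.

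**The concern.** A paired test without imputation can use a patient at a given cycle only if that patient has a form at baseline and at that cycle. The set behind each estimate therefore shrinks from cycle to cycle, and the estimates do not describe the same patients. Several of the listed reasons for leaving are plausibly tied to worse HRQoL, and section 7.2 itself says that adverse events influence quality of life during treatment.

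The primary objective in section 8.1 concerns the effect of treatment on patients' HRQoL, not only on those still completing forms at a late cycle. If patients who are getting worse leave first, the mean change at later cycles is biased towards no harm. Nothing in the plan would show whether this has happened: there is no longitudinal model, completion table by reason, rule for deaths or sensitivity analysis.

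**Working it through.** **The plan's own figure.** 300 × 0.50 = 150, which reproduces the number in section 9.5. It counts patients expected to complete their questionnaires over the treatment period. It is not the proportion retained at any cycle, and the documents give no such proportion.

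**Bias formula.** At a given cycle, let p be the proportion of all patients with a form, s their mean change and d the mean change in the rest. The all-patient mean is p·s + (1 − p)·d, while the paired analysis estimates s. The difference is s − [p·s + (1 − p)·d] = (1 − p)(s − d). With gap g = s − d, and with p and g both assumed:

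| p | g = 5 | g = 10 | g = 20 |
|---|---|---|---|
| 0.7 | 1.5 | 3.0 | 6.0 |
| 0.5 | 2.5 | 5.0 | 10.0 |
| 0.3 | 3.5 | 7.0 | 14.0 |

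**Comparison with precision.** With 150 pairs, two-sided 5% and 80% power, the detectable change is (1.96 + 0.84) × SD/√150. For an assumed SD of change of 15, 20 or 25, this is 3.4, 4.6 or 5.7 points. A bias of 5 points exceeds the first two and is close to the third.

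**Illustrative simulation.** The assumptions, none of them from the documents except the 300 patients, are: 12 follow-up visits, baseline SD 18, residual SD 12, slope SD 1.2 per visit and a true mean change of −6.0 at visit 12. Dropout depends on the last observed change, with strength given as logit per point.

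| Dependence | Retained at visit 12 | Paired mean change | Coverage of 95% CI |
|---|---|---|---|
| none | 50% | −5.9 | 95% |
| 0.01 | 50% | −4.3 | 83% |
| 0.03 | 85% | −4.8 | 87% |
| 0.03 | 70% | −3.5 | 60% |
| 0.03 | 50% | −1.3 | 26% |
| 0.05 | 50% | about +1 | about 1% |

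Repeat runs differ by a few tenths of a point. A random intercept and slope model recovers about −6.0 when dropout depends on observed scores. That is partly built in, because the simulated trajectories have the form that the model fits. When dropout depends on the unobserved current value, the model gives −3.9 and the paired test +1.7. The model then removes only part of the bias, which is why a sensitivity analysis is also needed.

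**End of Study form.** Under the same assumptions at 50% retained (0.03 and 0.05), with one form just after stopping, the baseline to End of Study pairs give −4.2 against a true mean at those times of −4.2 and −4.1. They represent the stoppers, but at each patient's own stopping time, so they do not estimate the visit-12 change of −6.0.

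**The case against.** - **The plan is descriptive.** Section 7.3 says so and rules out inference, and the sample size rests on feasibility. No confirmatory claim depends on the tests, which lowers the severity. It does not remove the problem: 9.7.2.1 sets a significance level, 9.7.2.4 plans t-tests, and a descriptive mean from a selected set misleads in the same way.
- **Drop-outs do complete a form.** Section 9.7.2.4 refers to follow-up times in general and excludes no visit, and the End of Study form reaches many stoppers. A reader might infer that deterioration in stoppers is hidden altogether. The documents do not support that: it is collected once but has no stated place in the analysis. Patients who die or do not attend are still missed.
- **The 50% is not retention.** A reader might infer that the plan expects half the patients to be gone by a late cycle. Section 9.5 does not say this; a patient who stops early but completes every form may count as a completer.
- **Not all missingness is informative.** Patient or investigator decision need not reflect worse HRQoL. Some truncation is administrative: enrolment closes in December 2019 and the study ends in December 2020, which allows the last patients about 365/14 ≈ 26 two-week cycles against a cap of 56.
- **The target is not stated.** The −6.0 is the mean for all 300 patients at a fixed time. Sections 9.3.2 and 9.7.2 speak of scores reported during treatment, so an all-patient target is a choice to be stated and justified.

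**Conclusion.** The concern holds in a conditional form and should be fixed. The mechanism follows directly from 9.7.2.2 and 9.7.2.4: each by-cycle estimate rests on patients with both forms, and no planned analysis examines the consequence. If stopping goes with worsening HRQoL, the change is biased towards no harm by (1 − p)g. That direction is a reasonable expectation from the listed reasons for leaving; it is not a result in the documents.

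The size is not established. Under the assumptions shown, it runs from about 1 point to a reversal of sign, and it is nil if dropout is unrelated to HRQoL. A reader might infer that the t-test interval will exclude the true value. That occurs in most runs only with strong dependence and low retention; at 85% retained, or with weak dependence, coverage stays between 83% and 87%.

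**What to change.** 1. In 9.7.2.4, make the primary estimate a likelihood-based mixed model for repeated QLQ-C30 scores. Use all baseline, on-treatment and End of Study questionnaires, placed at their actual time from Day 1 of Cycle 1. Take time as categorical or flexible, since a single straight line over up to 56 cycles is untested. Fix a time horizon with adequate numbers and report mean change with a 95% CI.
2. State the estimand, including that scores after death are not estimated. An ordinary mixed model implicitly projects trajectories past the last form, so the text must say how recorded deaths before the horizon are handled.
3. Keep the paired summaries as descriptive tables, with n and completion by visit and by reason. Report the baseline to End of Study change as a separate comparison.
4. Replace "Not applicable" in 9.7.2.5 with a delta-adjusted (pattern-mixture) sensitivity analysis by reason for stopping. Treat patients who reach cycle 56 or the administrative end of study separately.

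The mixed model needs no imputation, so 9.7.2.2 can stand for the main analysis; it needs an exception if the sensitivity analysis imputes. The cost is wording and standard software, with no new data. The drawbacks are that a missing-at-random assumption must be stated and that the estimate may look less favourable.

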- Adult ( $\geq$  18 years old) RAS wild-type metastatic colorectal cancer patients candidate to receive FOLFOX or FOLFIRI plus Panitumumab or FOLFOX or FOLFIRI plus cetuximab as upfront treatment as per clinical practice.
- Willingness and ability to comply with the protocol
- Written informed consent to study procedures

Exclusion criteria:

- Patients receiving a treatment under clinical investigation may not be included in the study.
- Previous treatment with an anti-EGFR monoclonal antibody.

- Follow-up

Not applicable

- Variables and end-point

- *Outcome Variable(s)*

HRQoL will be measured using the EORTC QLQ-C30 questionnaire. EORTC QLQ-C30 scores reported during the treatment will be also expressed as percentage of the scores reported at baseline.

Skin satisfaction will be measured using the DLQI. The DLQI score will also be expressed as a percentage of the maximum possible score of 30. DLQI scores reported during the treatment will be also expressed as percentage of the DLQI scores reported at baseline.

Tolerability: The toxicity rate, defined as the percentage of patients, relative to the total of enrolled subjects, experiencing a specific adverse event of any grade, according to National Cancer Institute Common Toxicity Criteria (NCI CTC-AE version 4.0), will be reported. Times to onset of dermatological toxicities will be also described.

Management of dermatological toxicity: concomitant medications, both topical and systemic, adopted to prevent or treat dermatological adverse events will be recorded.

- *ExposureVariable(s)*

Treatment adherence: The percentage of delayed cycles, the percentage of cycles administered with reduced doses, the number of administered cycles, the median treatment duration and the average relative dose intensity of every planned drug will be reported.

- Study Sample Size

The sample size calculation is based on feasibility considerations.

A total sample size of 300 patients (10-12 pts/center) has been planned for this study: it is estimated that about 50% (150 pts) of them should be able to complete the QoL questionnaires during the whole treatment period. This population is estimated relevant from the scientific board and useful for a first evaluation on variability of QoL during the follow-up.

- Data Analysis

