## 7.3 Statistical Inference (Estimation or Hypothesis[es])

No formal hypothesis will be tested in this study. Statistical analyses will be descriptive only. No statistical inference is planned.

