## 9. Research Methods

### 9.1 Study Design

This is a national, multicentric, prospective, observational trial. The decision to prescribe FOLFOX or FOLFIRI plus panitumumab or FOLFOX or FOLFIRI plus cetuximab must have been freely taken by the clinician prior to the study entry for each patient included. Each physician will see his/her patients within the context of routine visits, without any special visit being organized for the purposes of the study. Therefore, the doctor-patient relationship and patient follow-up are not modified. Physicians are totally free to decide on their patients' therapeutic management.

EORTC QLQ-C30 and DLQI questionnaires will be completed by the patients at baseline (Day 1 of Cycle 1), at the first day of every other cycle (every 2 weeks) thereafter, and at "End of Study Visit" (within 28 days from the end of treatment with anti-EGFR or withdrawal from study for any reason).

Before every cycle, adverse events will be recorded and graded according to NCI CTCAE Version 4.0. Treatment's modifications in terms of cycles' delay, dose reductions or drugs' interruptions will be recorded. Concomitant approaches to prevent or treat dermatological toxicities during the treatment will be registered.

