## 9.2.2 Selection and Number of Sites

Around 33 Italian Oncology Centers will participate to the study.

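### The between-group analyses in 9.7.2.4 specify no centre term, although drug and skin care are chosen by physicians in about 33 centres, so their p-values can be too small

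*Combined protocol and SAP*

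**What the plan says.** Section 9.7.2.4 plans three kinds of between-group analysis.

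- Panitumumab and cetuximab groups are compared on QLQ-C30, and again on DLQI: "Differences in mean between the two subpopulation will be tested at different times with T-test".
- The number of adverse events is related to treatment by an ANOVA.
- Skin toxicity events are related to prophylaxis in a last item that reads, in part, "QoL and presence of preemptive treatment will be tested with a multivariate analysis (Logistic".

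Section 9.7.2.1 adds: "The level of significance will be set to" p < 0.05. Section 7.3, on the other hand, states: "No statistical inference is planned".

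On the setting, section 9.2.2 says "Around 33 Italian Oncology Centers will participate to the study". Section 9.1 leaves the antibody to the clinician, and on management it begins "Physicians are totally free to decide on their" and goes on to patients' therapeutic management. Prophylaxis of skin toxicity is recorded as yes or no (9.3); it is not assigned.

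Centre is not named as a factor, stratum, random effect or cluster anywhere. The only stratification is by treatment (9.7.2.1). Covariates (9.3.3), stratified analysis (9.7.2.5.2) and sensitivity analysis for confounding and bias (9.7.2.5.3) are marked as not applicable. The planned summaries are means, standard deviations, medians and quartiles; no confidence interval is planned.

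**The concern.** A two-sample t-test takes its standard error from patients who are independent of one another. Patients of one centre share its physicians, its supportive care and, for adverse events, its recording and grading. If centres also differ in which antibody they use, or in whether they give skin prophylaxis, part of the contrast between groups is a contrast between centres. The t-test does not count that source of variation.

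The result would be drug or skin-care differences declared significant too often, some of them only differences between centres. This matters most for preemptive against reactive skin treatment, which is a stated secondary objective (8.2). Limiting the number of tests, or adjusting for patient characteristics, would not repair it.

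**Working it through.** **Inputs from the documents.** There are about 33 centres (9.2.2) and the level is 0.05 (9.7.2.1; two-sided assumed, as sidedness is not stated). Section 4 states: "A total sample size of 300 patients (10-12 pts/center) has been planned for this study". Section 9.5 adds that "it is estimated that about 50% (150 pts) of them should be able to complete the QoL questionnaires".

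**The plan's own figures.** 300 × 0.5 = 150 reproduces. The 300 itself rests on feasibility, so no power formula can reproduce it. The per-centre figure does not fit: 33 × 10 = 330 and 33 × 12 = 396. I use 300/33 = 9.09 patients per centre, and 150/33 = 4.55 for completers.

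**Assumed, because the documents are silent.** The outcome ICC is taken as 0.01 to 0.10. Exposure clustering is taken from 0 (same drug mix in every centre) to 1 (one drug per centre).

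**Formulas.** With m patients per centre:

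- design effect D = 1 + (m − 1) × ICC(outcome) × ICC(exposure)
- actual error = 2 × [1 − Φ(1.96/√D)]
- effective N = N/D

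Example with N = 300, ICC 0.05 and exposure wholly set by centre: D = 1 + 8.09 × 0.05 × 1 = 1.405; √D = 1.185; 1.96/1.185 = 1.654; actual error 9.8%.

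**Exposure wholly set by centre:**

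| N | ICC | D | True SE / naive SE | Effective N | Actual error |
|---|---|---|---|---|---|
| 300 | 0.01 | 1.081 | 1.040 | 278 | 5.9% |
| 300 | 0.05 | 1.405 | 1.185 | 214 | 9.8% |
| 300 | 0.10 | 1.809 | 1.345 | 166 | 14.5% |
| 150 | 0.01 | 1.035 | 1.018 | 145 | 5.4% |
| 150 | 0.05 | 1.177 | 1.085 | 127 | 7.1% |
| 150 | 0.10 | 1.355 | 1.164 | 111 | 9.2% |

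**Half that exposure clustering (0.5), ICC 0.01 / 0.05 / 0.10:** 5.5%, 7.4% and 9.8% at N = 300; 5.2%, 6.0% and 7.1% at N = 150.

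**Check by simulation** of the plain t-test with a normal outcome, 33 equal centres and no true difference (6000 runs per setting):

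- Exposure wholly set by centre: 6.0%, 9.1% and 14.6% at N = 300, and 5.3%, 7.9% and 9.8% at N = 150, for ICC 0.01, 0.05 and 0.10.
- Same drug mix in every centre: 4.8% to 5.3%, so no inflation.
- No centre effect: 4.8% to 5.7%.

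**Unequal centres.** A second simulation let centre sizes vary (2000 runs per setting). With a coefficient of variation of 0.6 and exposure set by centre, the error at N = 300 was about 13% at ICC 0.05 and 20% at ICC 0.10. At N = 150, across equal and unequal centres, it was 8-9% and 10-12%. Cluster-robust standard errors kept the error at 5-8% throughout.

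**Scope of these figures.** They are for the two-sample t-test. A one-way ANOVA with two groups is the same test, but the event-count ANOVA may contain other factors. The logistic analysis was not simulated; the mechanism is the same, but its size there is not shown.

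**The case against.** The strongest reply is that section 7.3 declares the analyses descriptive, drug against drug is not a listed objective (8.1, 8.2), and section 9.1 leaves the choice to the clinician for each patient without describing any centre policy. The first part does not dispose of the matter, because the current text still prescribes tests and a significance level, and p-values that are produced should be valid. The last part stands: freedom of choice makes differences between centres plausible but does not document them. The statement in 9.9.1 that patients are recruited sequentially concerns selection of patients, not dependence within centres.

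A reader might infer several stronger things that the documents do not support.

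- **That planned confidence intervals are too narrow.** None is planned. The fault lies in standard errors and p-values, and would pass to any interval added.
- **That the effective sample is close to the number of centres.** Even with exposure wholly set by centre, it is about 258, 214 and 166 of 300 at ICC 0.02, 0.05 and 0.10.
- **That the error at least doubles from ICC 0.05.** With about 150 completers it is about 7-9% there.
- **That the primary paired t-test fails in the same way.** It has no between-group exposure, and differencing removes a stable centre level. It would be affected only if changes from baseline cluster by centre, a separate condition on which the documents give nothing.
- **That the ANOVA and logistic model certainly ignore centre.** Their factors are not listed, so the accurate statement is that no centre term is specified.
- **That local grading biases the QLQ-C30 and DLQI comparisons.** Patients complete these questionnaires themselves; local grading bears on the event analyses only.

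**Conclusion.** The point holds for the between-group analyses in 9.7.2.4, conditionally and at moderate size. It requires that outcomes vary by centre and that drug or prophylaxis choice does too. Both are plausible from the design, and neither is documented.

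For ICC 0.01 to 0.10, exposure wholly set by centre and centres of about equal size, the actual two-sided error is about 6-15% with 300 patients and about 5-10% with 150. Taking in unequal centres as well, the range with 150 is about 7-9% at ICC 0.05 and 9-12% at ICC 0.10. The 300-patient figures suit early visits with nearly complete questionnaires; the 150-patient figures suit analyses of those who complete throughout. Partial clustering gives less, and an equal mix in every centre gives none.

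This is a cheap improvement to secondary comparisons, not a fault in the primary analysis.

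**What to change.** In 9.7.2.4, for the drug comparisons, the event-number analysis and the preemptive-treatment analysis only:

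1. Use the matching regression (linear, count or logistic) with a random intercept for centre, or cluster-robust standard errors by centre with small-sample degrees of freedom.
2. Report each group difference with the 95% confidence interval from that model.
3. Tabulate, by centre, the share of patients on each drug and on baseline prophylaxis. This shows whether exposure does follow the centre.
4. State in the report that this corrects the variance but does not fully remove confounding by centre, least of all if exposure proves to be wholly set by centre.

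The cost is analysis wording and a few lines of code. Site staff enter the data (9.4), so centre is known and nothing new need be collected. Intervals will be somewhat wider where centre practice differs.

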#### 7.1 Diseases and Therapeutic Area

Different options are currently available as upfront choices for the systemic treatment of metastatic colorectal cancer patients. In the last years different phase III trials investigated the addition of a drug targeting the Epidermal Growth Factor Receptor (anti- EGFR) to a first-line chemotherapy doublet, leading to the approval of two anti-EGFR monoclonal antibodies: the chimeric human-murine IgG1 cetuximab and the fully human IgG2 panitumumab.

The prospective and *post-hoc* analyses of randomized trials of first-line chemotherapy with or without an anti-EGFR monoclonal antibody, show that patients bearing a mutation in *KRAS* codon 12 or 13 do not benefit from the addition of the anti-EGFR to the upfront chemotherapy doublet, so that the use of both cetuximab and panitumumab has been restricted to *KRAS* wild-type patients. More recently, a pre-specified analysis of results of the PRIME trial showed for the first time that also patients bearing a mutation in some hotspots of *KRAS* (other than codon 12 and 13) and *NRAS* genes (ie, codon 12, 13, 59, 61, 117 and 146) do not achieve benefit from the addition of cetuximab or panitumumab to first-line chemotherapy. A potential detrimental effect of adding anti-EGFRs to first-line FOLFOX was also suggested in mutated patients. On the other hand, the efficacy of anti-EGFR monoclonal antibodies was optimized in patients not bearing any mutation in *KRAS* or *NRAS* codon 12, 13, 59, 61, 117 and 146, defined as *RAS* wild-type patients. Based on these results, the European Medicines Agency further

restricted the use of both panitumumab and cetuximab to this subgroup of patients. In March 2015, the European Medicines Agency approved the extension of indication for Panitumumab FOLFIRI in 1st line. The new indication was implemented by Italian Medicines Agency on 24 February 2017.

Therefore doublet plus panitumumab or cetuximab are valuable options for the upfront treatment of *RAS* wild-type mCRC patients.

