## 9.2.4 Matching

Not applicable

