### 9.3.3 Covariate Assessment

*Not applicable*

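### The between-drug t-tests on QLQ-C30 and DLQI are unadjusted although clinicians choose the drug, so a panitumumab–cetuximab difference cannot be attributed to the drug

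*Combined protocol and SAP*

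**What the plan says.** Section 9.7.2.4 scores the QLQ-C30 in the whole population and in "two subgroups: FOLFOX/FOLFIRI plus panitumumab and FOLFOX/FOLFIRI plus cetuximab". It then says: "Differences in mean between the two subpopulation will be tested at different times with T-test". The same sentence follows for the DLQI. No covariate is named.

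Allocation is not randomised. Under section 9.1 the choice of regimen "must have been freely taken by the clinician prior to the study entry for each patient included".

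Every section where control of confounding could appear is left empty. Section 9.3.3 (Covariate Assessment) reads "Not applicable", and the same entry stands under 9.2.4 (Matching), 9.7.2.5.2 (Stratified Analysis) and 9.7.2.5.3 (Sensitivity Analysis for Residual Confounding and Bias). The only safeguard stated, in 9.9.1, is sequential recruitment.

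On first-line panitumumab plus FOLFIRI, section 7.1 says: "The new indication was implemented by Italian Medicines Agency on 24 February 2017". Section 9.2.1 runs enrolment from about November 2015 to December 2019. Section 7.1 lists cetuximab with irinotecan-based chemotherapy and with first-line FOLFOX, and describes no change during the study.

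Two other sections do not fit 9.7.2.4. Section 7.3 says the analyses are descriptive with no inference, while 9.7.2.1 sets a 0.05 significance level. Section 9.7.2.1 also names strata by drug with FOLFOX only, while 9.7.2.4 pools the two backbones.

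**The concern.** When the clinician picks the drug, the two groups can differ in backbone, performance status, disease burden, baseline quality of life, centre and enrolment year. A two-sample t-test at a follow-up visit compares the groups with all of those differences left in. Sequential recruitment limits selection into the study but does nothing about who receives which drug. The ANOVA and logistic analyses in 9.7.2.4 address tolerability, event counts and preemptive skin treatment. They name no confounders and do not replace the t-tests.

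The indication date adds a specific route. Before it, labelled first-line panitumumab use meant FOLFOX, whereas cetuximab was labelled with either backbone. Drug, backbone and calendar time may therefore be linked.

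At stake are prespecified p-values, placed beside the primary analysis, that set the sponsor's product against a competitor. Section 7.2 says quality of life matters especially when choosing between options with no clear advantage, so readers are likely to use them that way.

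**Working it through.** **The plan's own figures.** Section 9.5 expects about half of 300 patients to complete the questionnaires: 300 × 0.50 = 150, as stated. From 1 November 2015 to 31 December 2019 is 1,521 days, or 1,521 / 30.4375 = 49.97 months, matching the stated 50. The plan gives no SD, effect size, power or drug split.

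**Time before the indication.** From 1 November 2015 to 24 February 2017 is 481 days = 15.8 months, and 481 / 1,521 = 0.316 of the window.

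**Assumptions (none from the documents).** Uniform accrual; labelled use only; the same FOLFIRI share *f* for both drugs whenever both backbones are available, *f* = 30%, 50% or 70%; backbone effect *g* = 5 or 10 points on a 0–100 QLQ-C30 scale; SD 20 or 25; no true drug effect; two-sided 0.05. Group size *n* is 75 per drug (150 completers split equally) or 150 per drug (all 300 observed and split equally).

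**Formulas.**
- Gap in FOLFIRI share from the date alone = 0.316 × *f*
- Bias *b* = gap × *g*
- SE = SD × √(2/*n*)
- Chance of p<0.05 = 1 − Φ(1.96 − *b*/SE) + Φ(−1.96 − *b*/SE)

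Example: *f* = 70%, *g* = 10, SD 20, *n* = 150. Gap = 0.221; *b* = 2.21; SE = 20 × √(2/150) = 2.31; *b*/SE = 0.957. Chance = 1 − Φ(1.003) + Φ(−2.917) = 0.16.

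| Gap in FOLFIRI share | Bias (points) | Chance, 75 per drug | Chance, 150 per drug |
|---|---|---|---|
| 9.5 points (*f* = 30%) | 0.47–0.95 | 5.2–6.0% | 5.3–7.0% |
| 15.8 points (*f* = 50%) | 0.79–1.58 | 5.4–7.7% | 5.9–10.5% |
| 22.1 points (*f* = 70%) | 1.11–2.21 | 5.8–10.4% | 6.7–16.0% |
| 50 points (assumed prescriber preference) | 2.5–5.0 | 9.4–33.4% | 13.9–58.1% |

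The first three rows are what the date alone can produce. The last needs a preference on which the documents are silent.

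**Does adjustment help?** This was simulated with 4,000 trials per scenario: SD 20, baseline-to-follow-up correlation 0.5, FOLFIRI share 20% versus 70%, backbone effect 5 points, no drug effect.
- Unadjusted t-test: mean spurious difference about 2.5 points; p<0.05 in 12% (75 per drug) or 19% (150 per drug).
- With a further 5-point baseline imbalance: about 5 points; 33% or 57%.
- ANCOVA on drug, backbone and baseline score: mean difference about 0; about 5% in each of these scenarios.

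The ANCOVA matches how the data were generated, so this shows what adjustment does for measured factors only. No figure is offered for the DLQI, since the documents give nothing on which to scale one.

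**The case against.** **The comparison is peripheral.** Neither section 8.1 nor 8.2 lists a drug comparison, the main analysis is paired within patients, and section 7.3 disclaims inference. This stands and lowers the severity. It does not remove the tests, which 9.7.2.4 prespecifies.

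**The backbone link may not have existed.** A reader might infer from the February 2017 date that the documents prove a built-in backbone imbalance. They do not. Actual use by drug, backbone and period is not reported, and the eligibility rules of the 2015 protocol are not shown. The FOLFOX-only strata in 9.7.2.1 may be residue of a FOLFOX-only design; if so, the early imbalance shrinks or vanishes. Free choice of drug remains a source of confounding either way.

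**The bias could be small.** A reader might infer a FOLFIRI gap of 30 points or more from the date. Under the assumptions above that would need a FOLFIRI share of about 95% (0.30 / 0.316). The date alone gives 9 to 22 points and a modest bias.

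**The test itself is not invalid.** A reader might say its type I error is not 5%. For equality of the observed group means, confounding alone does not change the level. What rises is the chance of a significant difference when the drugs have the same effect, and that is how the figures here should be read.

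**Conclusion.** The point holds in a limited form. Following 9.7.2.4 yields p-values for panitumumab against cetuximab that cannot be attributed to the drug. That follows from the text alone: free choice, pooled backbones, and no matching, covariates, stratification or sensitivity analysis.

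The size and direction of any bias cannot be derived from the documents. Under the stated assumptions, the indication date alone gives about 0.5–2.2 points and a 5–16% chance of a spurious difference over 75–150 per drug, against a nominal 5%. A 50-point gap gives 2.5–5 points and 9–58%. The 150-per-drug figures are the extreme case, because they need every patient observed and an equal split.

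It would go too far to say that every observed difference is confounded by a known amount, or that the primary result is affected. The paired change from baseline does not depend on this comparison. Severity: should fix.

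**What to change.** Take one of two routes in 9.7.2.4.

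1. **Adjust.** Replace both between-drug t-tests with a prespecified longitudinal model containing at least the baseline value of the same score and the backbone, plus ECOG, age, sex, metastatic sites, enrolment period (before or after 24 February 2017) and centre. List these in 9.3.3. Report adjusted differences with 95% confidence intervals as exploratory associations, and say that only measured factors are adjusted for.
2. **Describe.** Drop the between-drug p-values and present the groups descriptively with a caveat on confounding, consistent with section 7.3.

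In either case reconcile sections 7.3, 9.7.2.1 and 9.7.2.4: no inference against tests at 0.05, and FOLFOX-only strata against pooled FOLFOX/FOLFIRI groups.

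The cost is wording, some extra analysis work and a few degrees of freedom. Section 9.3 already collects date of birth, sex, metastatic sites, first-line schedule, ECOG and both baseline questionnaires. Centre is not itemised there, but the site number appears on the safety form in Appendix B. Enrolment period can be taken from the consent date, which section 10.1 requires on the form. No new patient assessments are needed.
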